11.6.3 Early Termination of Subjects from the Study

All participants have the right to withdraw from the study at any time.

In addition, subjects may be withdrawn from the study by the PI or designee for the following reasons:

- AEs.
- Subject has a positive urine drug or alcohol result.
- Difficulties in blood collection.
- Pregnancy.
- Disease progression which requires discontinuation of the study intervention.
- If the participant meets an exclusion criterion (either newly developed or not previously recognized) that precludes further study participation.

The PI, in consultation with the Medical Monitor, may withdraw any subject from the study treatment, if, in the investigator's opinion, it is not in the subject's best interest to continue. A subject may be withdrawn by the PI (or designee) or the Sponsor/Medical Monitor if enrollment into the study is inappropriate, the study plan is violated, or for safety reasons.

If withdrawn from the study, participants will be required to return all remaining study drug. A mailing address will be provided to the participant upon withdrawal. If withdrawn, the participant will still need to provide a blood sample locally and have a remote TEAE assessment 7 ± 2 days post-withdrawal from the study. A study investigator will contact participants by telephone to remind them of upcoming, scheduled local phlebotomy appointments. The participant will also need to have a remote TEAE assessment 14 ± 2 days post-withdrawal from the study. Participants local to the study site will have the option of completing AE assessments at the NIH. If a participant is withdrawn for a safety reason(s), more intensive safety monitoring may be undertaken as clinically indicated.

11.7 Study Restrictions

11.7.1 Prohibitions and Concomitant Medications

Consumption of foods and beverages containing the following substances will be prohibited as indicated:

- Xanthines/Caffeine: 24 hours before administration of the first and final S 48168 doses continuing through the last PK sample collection for that day (small amounts of caffeine derived from normal foodstuffs e.g., 250 mL/8 oz./1 cup decaffeinated coffee or other decaffeinated beverage, per day, with the exception of espresso; 45 g/1.5 oz. chocolate bar, per day, would not be considered a deviation to this restriction);

- Alcohol: 48 hours before administration of the first and final S 48168 doses continuing through the last PK sample collection for that day;

Concomitant medications will be prohibited as listed in the exclusion criteria in [Section 11.6.2](#). Once the subject has been dosed, acetaminophen (up to 2 g per 24 hours) may be administered at the discretion of the PI or designee.

If deviations occur, the PI or designee will decide on a case-by-case basis whether the subject may continue participation in the study and may consult the Sponsor if needed.

All medications taken by subjects during the course of the study will be recorded.

11.7.2 Meals

Water and other fluids (except water provided with each dosing) will be restricted 1 hour prior to and 1 hour after their first and final S 48168 dose administrations but will be allowed ad libitum at all other times.

Subjects will fast overnight for at least 10 hours prior to their first and final S 48168 dose administrations and will continue the fast for at least 4 hours post-dose.

When confined in the NIH CC, meals and snacks will be provided at appropriate times, except when subjects are required to fast.

During confinement, each meal and/or snacks served at the NIH CC will be similar in caloric content and composition and will be taken at approximately the same time for all participants.

11.7.3 Activity

Subjects will remain ambulatory or seated upright for the first 4 hours following S 48168 (ARM210) dosing, except when they are supine or semi-reclined for study procedures.

However, should AEs occur at any time, subjects may be placed in an appropriate position or will be permitted to lie down.

Depending on the NIH CC rules and regulations, subjects may be prohibited from smoking during their confinement or during portions of their confinement.

11.8 Treatments

11.8.1 Treatments Administered

Research with an investigational drug

S 48168 (ARM210) requires an IND, and the FDA approved IND number is: [REDACTED] (See Appendix # 7). The company manufacturing S 48168 (ARM210) is Laboratoires Servier. Study drug will be shipped by Laboratoires Servier directly to the NIH Pharmacy as therapeutic units. The study sponsor is ARMGO Pharma Inc.

S 48168 (ARM210) will be supplied as 20 mg gastro-resistant tablets.

Study visits will be scheduled such that no more than two participants receive their initial dose in the same week (See Section 12.11.10 of this protocol for details). The first three participants were dosed with 120 mg S 48168 (ARM210) (6 x 20 mg tablets) daily for approximately 28 days (not to exceed 30 days). After DSMB review of the safety, tolerability and PK of the 120 mg dose, the remaining participants were dosed with 200 mg S 48168 (ARM210) (10 x 20 mg tablets) daily for approximately 28 days (not to exceed 30 days). All subsequent participants are planned to be dosed with \leq 200 mg S 48168 (ARM210) (10 x 20 mg tablets) daily for approximately 28 days (not to exceed 30 days). The tablets are small in size (5 mm diameter).

Study investigators will administer S 48168 (ARM210) during the time the participant is confined to the NIH CC for 24h PK assessments (first and final dose administrations). S 48168 (ARM210) should be administered orally following an overnight fast (at least 10 hours) with approximately 240 mL of water on all PK days. A mouth check will be performed by the qualified designee to ensure that the subjects have swallowed the study drug. The exact clock time of dosing will be recorded using a standardized network clock.

Study investigators will instruct the participant in the proper dosing instructions for home administration when drug supplies are dispensed (Appendix # 8). Study drug (S 48168 [ARM210]) will be provided in tablet form. All participants will be instructed to self-administer the study medication daily with water in the morning. Compliance will be assessed during each phone/e-mail contact. Compliance will be verified at in-person visits for residual pill counts as well as with diary. Adequate compliance will be defined as taking 80% of the study drug. If a participant completely misses a dose (e.g. missed one day of drug), we will have them take the next dose and contact the site.

11.8.2 Method of Assigning Subjects to Treatment

Individuals who have expressed an interest in participating and meet the pre-screening eligibility criteria will be contacted for telephone screening as detailed in Appendix # 2. Each individual will be assigned a unique identification number (baseline number) at this time.

The individuals who complete the study screening assessments at NIH and meet all the eligibility criteria (Appendix # 3) will receive an allocation number. The allocation number will be different from the baseline number. If replacement subjects are used, the replacement subject number will be 100 more than the original (e.g., Subject No. 101 will replace Subject No. 1). Eligible participants will be started on \leq 200 mg/day dose.

11.8.3 Blinding

This is an open label study.

11.8.4 Interim Analysis (PK)

Interim PK analysis was conducted by Nuvisan (contract vendor) as follows:

First dose group (120 mg/day): Full PK analysis once the first three participants completed dosing for approximately 28 days (not to exceed 30 days). This allowed verification that the observed PK results from these *RYR1*-RM affected individuals agreed with PK results from previous studies in healthy volunteers and that the Cmax limit of 35 ug/mL was not exceeded. At this stage of drug development, a PK value that would not require a dose adjustment would be considered as similar. This would mean 50% lower or 200% higher than that of healthy volunteers.

Based on PK results and safety data from the first dose group, the dose to be administered in subsequent participants was increased to 200 mg/day. This was based on DSMB recommendations and investigator and sponsor's joint decision.

Second dose group (200 mg/day): PK analysis for Cmax once the first three participants have completed dosing for approximately 28 days (not to exceed 30 days). This will allow verification that the Cmax limit of 35 ug/mL was not exceeded. Subsequently, all remaining samples will be shipped to the contract laboratory for analysis at the end of the study, when full PK analysis beyond the Cmax measurement will occur for all of the samples obtained from this group

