9.5 Dose Justification

The initial proposed dose for this study was 120 mg S 48168 (ARM210) daily for approximately 28 days (not to exceed 30 days) for the first three participants (6 x 20 mg tablets) (see details outlining dose modification in Section 9.6). An additional three participants were dosed with 200 mg S 48168 (ARM210) (10 x 20 mg tablets) daily for approximately 28 days (not to exceed 30 days) after DSMB evaluation of the interim safety and PK data. The remainder of participants will be dosed at the same high dose \leq 200 mg S 48168 (ARM210) (10 x 20 mg tablets) daily for approximately 28 days. The projected exposure at 200 mg/day dose remains below preclinical safety margins ($C_{max} < 35$ ug/ml), as well as below the highest dose tested in healthy volunteers (240 mg/day for 14 days). Preclinically, the one finding that is not monitorable in humans is the proconvulsant risk, with convulsions rarely observed at highest dose level in dogs in the 39-week study. The convulsions occurred at the high dose of 250 mg/kg/day in the 39-week GLP chronic study. The C_{max} of that dose for both genders is 374 ug/ml. This concentration range is associated with an *in vivo* unbound fraction of 3.5%, which is greater than 20-fold higher than the *in vivo* fraction unbound (0.16%) in the human at 240 mg. It is likely that this high unbound fraction, which is able to penetrate tissues, including the brain, was responsible for the rare convulsions seen in 1 of 20 dogs (i.e. 1/12 dogs from the 39-week study and 0/8 dogs from the 13-week study, both studies at 250 mg/kg/day). The FDA has determined that the high dose (250 mg/kg/day from 13-week dog study) sets the NOEL for convulsions for this trial. The C_{max} at the NOEL (from the 250 mg/kg high dose) from the 13-week dog study is a mean of 320 ug/ml for both sexes. In consultation with the FDA, the current dose cap is at 35 ug/ml for C_{max} to provide a significant margin to the NOEL C_{max} from the dog.

In the first in man study [REDACTED] 40 male healthy volunteers (5 groups, approximately 8 participants per group) : placebo) completed the study part I (single escalating dose). Five dose levels were tested successively: 20 mg, 60 mg, 120 mg, 240 mg and 400 mg. In part II, four dose levels were studied with daily doses for 14 days (20 mg/day, 60 mg/day, 120 mg/day and 240 mg/day) all of which were well tolerated.

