Using total PK to determine the safety margin, the Cmax should be limited to 35 ug/ml per the FDA partial clinical hold comments. This limit is based on a 10-fold safety margin to the Cmax of the high dose of the 13-week dog toxicology study. We propose to dose the first three participants at 120 mg/day. The mean Cmax for healthy volunteers at this dose was 17 ug/ml. Assuming the safety, tolerability and PK are acceptable [REDACTED]

[REDACTED] to the DSMB, a top dose of \leq [REDACTED] (not to exceed 30 days) is proposed for the remaining participants.

Preliminary human PK of 14 days of dosing at 240 mg/day S48168 (ARM210) shows a mean Cmax of 35 ug/ml [REDACTED]. The Cmax at steady state has been dose proportional, with no evidence of non-linearity, with low variability (13.5%). The projected Cmax for 200 mg/day at steady state is 28 ug/ml. Assuming that the PK at 120 mg/day dose is similar to the previous numbers seen in healthy volunteers, then a dose \leq 200 mg/day should remain below the dose cap of 35 ug/ml.

Staggered dosing was implemented for the first three participants at the low dose level, starting each participant on drug after the previous participant had finished 14 days of dosing. At the high dose level (200 mg/day), Cmax at steady state of each participant was measured before dosing the next participant. S48168 (ARM210) reaches steady state typically after five days of dosing, consistent with its terminal half life. PK profiles have been established in RYRI-RM trial participants at both low and high dose levels and are consistent with healthy volunteer studies. In addition, none of the subjects tested so far have exceeded the FDA Cmax limit of 35 ug/ml at steady state and no clear safety signals have been observed to date in safety labs, EKG, or other safety related assessments.

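### The SAP sets 200 mg patients beside 240 mg volunteers with no dose-normalised parameter, and the two-fold exposure criterion, if applied to Cmax at 200 mg, is wider than the 35 µg/mL cap allows (exploratory PK conclusion only)

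*Protocol*

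**What the plan says.** **Criterion.** Protocol 11.8.4, in its paragraph on the 120 mg interim analysis, states that "a PK value that would not require a dose adjustment would be considered as similar. This would mean 50% lower or 200% higher" than in healthy volunteers. SAP 4.2 has the same text, also under the 120 mg group. Protocol 12.10.3 reaches further. There, a rise of roughly two-fold or a fall of about half in exposure counts as clinically meaningful, with no dose or parameter named. The section expects eight participants to suffice. Only the first three started at 120 mg, so the eight must include participants on 200 mg.

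**Meaning of exposure.** Protocol 9.5 uses the word for something judged against a Cmax margin ("The projected exposure at 200 mg/day dose remains below preclinical safety margins"), while 9.6.2 restates the food result as AUC. The hypothesis in 10.1 concerns steady-state exposure, and 10.2 lists both AUCtau and Cmax as Day 28 endpoints.

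**Cmax figures (9.5).** At 120 mg/day, "The mean Cmax for healthy volunteers at this dose was 17 ug/ml". At the highest repeated dose, "Preliminary human PK of 14 days of dosing at 240 mg/day S48168 (ARM210) shows a mean Cmax of 35 ug/ml". For the current dose, "The projected Cmax for 200 mg/day at steady state is 28 ug/ml". Cmax is capped at 35 µg/mL, and the dose drops to 180 mg/day if PK monitoring shows that the cap could be exceeded.

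**SAP comparison.** SAP Table 5.1 lists patients at 120 mg (A) and 200 mg (B), and volunteers at 120 mg (C) and 240 mg (D). SAP 3 names the 240 mg level for the comparison, with redactions around that sentence. Table 11-3 has one column per treatment, labelled with its dose. Neither the parameter lists nor the shells contain a dose-normalised parameter. SAP 7.7 makes the comparison descriptive.

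**The concern.** The 120 mg patients have a dose-matched volunteer group; the 200 mg patients do not. Their nearest comparator received 20% more drug. Read across the columns, any rise in patient exposure at 200 mg is partly hidden by the dose difference.

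The volunteer mean Cmax at 240 mg is itself 35 µg/mL, the value of the cap. Columns that look equal would therefore describe a patient group whose mean sits at the cap.

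The only numerical criterion for the overall comparison is two-fold/50% on an undefined exposure. A reader who applies it to Cmax at 200 mg could report no clinically meaningful difference at a ratio that protocol 9.5 treats as a reason to give 180 mg. Protocol 9.5 says that a phase II trial is being planned, so that statement may be relied on later.

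**Working it through.** **Inputs.** Volunteer mean Cmax: 17 µg/mL at 120 mg and 35 at 240 mg. Projected mean at 200 mg: 28. Cap: 35. Dose proportionality is stated. CV: 13.5% (all from protocol 9.5) or about 15% (12.10.3).

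**1. Reproduce the projected 28.**
- From 120 mg: 17 × 200/120 = 28.33 (1.2% above 28).
- From 240 mg: 35 × 200/240 = 29.17 (4.2% above 28).

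The printed figure is reproduced to within rounding from 120 mg and is slightly low against 240 mg.

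**2. Fold-rise at which the 200 mg mean reaches the cap.**
- From the printed mean: 35/28 = 1.25.
- Scaled from 120 mg: 35/28.33 = 1.235.
- Scaled from 240 mg: 35/29.17 = 1.20.

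Two-fold would be a mean of 56–58 µg/mL (2 × 28 to 2 × 29.17). At 120 mg, two-fold is 2 × 17 = 34, just under the cap. On the mean, then, the criterion fits 120 mg but not 200 mg.

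**3. What the SAP columns would show, 200 mg patients over 240 mg volunteers.**
- No disease effect: 200/240 = 0.83 for Cmax or AUC under proportionality. For Cmax with the printed projection it is 28/35 = 0.80.
- Understatement under proportionality: 1 − 200/240 = 17%.
- Apparent ratio 1.00: patient mean 35; dose-normalised ratio 1.00 × 240/200 = 1.20.
- Apparent ratio 2.0: dose-normalised ratio 2.0 × 240/200 = 2.4.

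**4. Individuals above the cap at 200 mg.** Assume lognormal Cmax with arithmetic mean m and s² = ln(1 + CV²). Then P(Cmax > 35) = 1 − Φ[(ln 35 − ln m + s²/2)/s]. Ranges cover CV 13.5% and 15%. The last column is (1 − P)³.

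| True dose-normalised ratio | Above 35, volunteer mean 28 | Above 35, volunteer mean 29.17 | None of 3 above 35 (mean 28) |
|---|---|---|---|
| 1.0 | 4–6% | 8–10% | 84–88% |
| 1.1 | 15–18% | 24–26% | 56–61% |
| 1.2 | 36% | 47% | 26–27% |
| 1.25 | 47% | 58–59% | 15% |
| 1.5 | 87–90% | 92–94% | 0.1–0.2% |

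Three 200 mg participants with none above the cap make 1.5-fold implausible. They do not exclude 1.1 to 1.25, the range in which the cap matters and a two-fold criterion is silent.

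**The case against.** **The quoted rule belongs to 120 mg.** This stands. The wording about no dose adjustment sits in the 120 mg paragraph, where the cap is a separate requirement, and two-fold of 17 is 34. The 200 mg paragraph has only the absolute cap. Reach to 200 mg Cmax rests on 12.10.3, which calls its bounds unclear until efficacy is established and says there is no specific hypothesis. The point is therefore conditional on how exposure is read.

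**The SAP computes no ratio and labels each column with its dose.** Also true. The 1.00 is what a reader would derive, not a planned output, and a careful reader could adjust by hand. But side-by-side columns are the comparison, and the adjustment is not printed. The redactions in SAP 3 mean that sentence alone cannot settle what was intended; Table 5.1 and the shells show what is tabulated.

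**Individual Cmax is already reported.** Table 14.2.1.8 lists it by subject, and Cmax above 35 µg/mL is an adverse event of special interest (12.10.7.7) counted in Table 14.3.1.4. A mean near the cap would show there. This stands and limits the consequence.

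**Stronger readings.** A reader might infer that the two-fold rule let unsafe doses through, or that a breach could pass unnoticed. The documents do not support this. At 200 mg, "Cmax at steady state of each participant was measured before dosing the next participant", an interim Cmax check was specified separately, and "none of the subjects tested so far have exceeded the FDA Cmax limit of 35 ug/ml at steady state". A reader might also question the step that begins "Assuming that the PK at 120 mg/day dose is similar to the previous numbers seen in healthy volunteers" and concludes that 200 mg stays below the cap. Similarity at 120 mg supports that step only up to a mean of 35 × 120/200 = 21 µg/mL, or 21/17 = 1.24-fold. But escalation followed independent review of the 120 mg safety and PK data, and Cmax has since been measured directly at 200 mg. That step is history, not a live defect.

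**Conclusion.** The point holds as a clarification to an exploratory, descriptive comparison. The 200 versus 240 mg display understates the patient/volunteer ratio by about 17%. Equal Cmax in those columns corresponds to a 1.20-fold dose-normalised rise, with about 47% of individuals above 35 µg/mL. If the two-fold bound in 12.10.3 is applied to Cmax at 200 mg, it exceeds what the cap allows, which is 1.25-fold from the printed mean of 28 and 1.20-fold only when scaled from 240 mg.

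The 17% and the 1.20 rest on dose proportionality. The shares above the cap also need a lognormal Cmax and a patient CV of 13.5–15%, taken from volunteers. Nothing here bears on the dose, the stopping rules or the primary endpoint. Most samples after the interim are assayed at study completion (12.10.10), but that timing is separate from this point and unchanged by it.

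**What to change.** 1. Add dose-normalised Cmax,ss and AUCtau for Treatments B and D (or all four) to SAP Table 11-3 and its source tables. Base the 200 mg patient–volunteer comparison on those rows, citing the dose proportionality stated in protocol 9.5. Protocol 13.1 and SAP 2.2 already allow additional parameters.
2. In protocol 12.10.3, state that the two-fold/50% bounds apply to dose-normalised AUCtau, and that steady-state Cmax at 200 mg is also judged against the 35 µg/mL cap, using the individual values and event counts already planned.
3. Leave the 120 mg interim text in protocol 11.8.4 and SAP 4.2 as the record of a completed decision, and disclose that the clarification was made after interim PK results were known.

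The cost is two extra table rows and a sentence or two of text, with no new samples. The downsides are reliance on dose proportionality and a disclosed late change in an open-label study. The cap, the 180 mg rule and adverse-event reporting stay as they are.

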11.8.5 Stopping Rules

A decision to stop dose administration or terminate the study will be made jointly by the Sponsor, Medical Monitor, Data and Safety Monitoring Board (DSMB), and the PI following the review of all pertinent safety/tolerability data and PK data (if available). However, the DSMB may independently decide to pause, halt, or terminate the study. In addition, the DSMB may independently decide to pause or stop dose administration in an individual.

To stop or temporarily halt dose administration in any subject:

- Participant has a SAE that is possibly or definitely related to drug.
- Participant has a non-serious adverse event that is possibly or definitely related to drug and is severe (on a scale of mild, moderate, or severe) per the Common Terminology Criteria for Adverse Events (CTCAE) Version 5.0.
- Participant has an AE special interest (AESI) that is considered serious as defined by 21 CFR 312.32. AESIs for this study are as follows:

Large increases in transaminases, Aspartate aminotransferase or Alanine aminotransferase. If the subject's baseline transaminases were within normal limits, then a change of 3X ULN is the criteria. If the subject's baseline transaminases are above the ULN at baseline, then 5X ULN would be the criteria. Baseline elevations in transaminases have been known to occur in some patients with *RYR1*-RM, likely due to muscle injury as a consequence of the disease and normal activity.

CNS toxicity (tremors/convulsions seen in safety assessment animals) - consider tremors and any symptoms of seizure as the events to monitor for.

Gastric toxicity - severe gastric or epigastric pain or severe vomiting.

Plasma Cmax (S 48168) >35 µg/mL.

Dosing may be temporarily halted in any subject for medically important non-serious AE that is possibly or definitely related to drug and requires medical intervention. Dosing may be halted until the AE resolves and then may be resumed with careful observation for reoccurrence. The PI, IRB, CD, the Sponsor (ARMGO Pharma Inc.), DSMB, or the FDA may pause, halt, or terminate the study at any time following review of any safety concerns.

The study will be terminated if:

- ≥ 2 subjects have a SAE that is possibly, probably, or definitely related to drug.
- ≥ 2 subjects have a medically important non-serious TEAE that is probably or definitely related to drug and is severe (on a scale of mild, moderate, or severe) per the Common Terminology Criteria for Adverse Events (CTCAE) Version 5.0.
- ≥ 3 subjects have a medically important non-serious TEAE that is possibly related to drug and is severe (on a scale of mild, moderate, or severe) per the Common Terminology Criteria for Adverse Events (CTCAE) Version 5.0.

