12.10.7.4 Reporting

All AEs that occurred during this clinical study will be recorded on the AE CRF using a recognized medical term or diagnosis that accurately reflects the event. For each adverse event, the investigator will provide the onset date, end date, intensity, treatment required, outcome, seriousness, and action taken with the investigational drug. The PI or designee will review each event and assess its relationship to drug treatment (likely, probably, possibly, unlikely or unrelated). Each sign or symptom reported will be graded in accordance with CTCAE (version 5), and the date of onset, time of onset, and outcome of each event will be noted. To fulfil the regulatory requirements for expedited safety reporting, the sponsor evaluates whether a particular AE is "listed" (i.e. known side effect of the drug or not). Medical judgment should be used to determine the causal relationship of adverse event, considering all relevant factors, including pattern of reaction, temporal relationship, de-challenge or re-challenge, confounding factors such as concomitant medication, concomitant diseases and relevant history. Serious AEs that are considered related to S48168 will be considered a suspected unexpected serious adverse reaction (SUSAR). Assessment of causal relationship must also be recorded on the CRF. If an AE has not resolved at the end of the study reporting period it will be documented as ongoing on the corresponding CRF.

Prompt reporting of adverse events is the responsibility of the PI or designee. The reporting period for AEs is the period immediately following each study administration through 28 days after each dose. AEs must be followed until resolution or stabilization, the subject is lost to follow-up, even if this extends beyond the 28-day post-dosing reporting period (for the purpose of obtaining a stop date for the event).

If an AE has not resolved at the end of the study reporting period it will be documented as ongoing on the corresponding CRF.

Each AE will be reviewed with the medical monitor, [REDACTED] and discussed with the PI. AEs will be reported to the DSMB, regardless of PI classification for review.

The AE severity definitions of CTCAE version 5 will be used for rating the severity of all AEs (Grade 1-5).

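### The stopping rules use a different causality scale from the AE reporting section, omit *probably* from the individual halts, and do not pool *possibly* with stronger attributions when counting toward termination

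*Protocol*

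**What the plan says.** **Grading scale.** Under Protocol 12.10.7.4 (Reporting), the PI or designee must review each event and "assess its relationship to drug treatment (likely, probably, possibly, unlikely or unrelated"). The scale has three positive grades and no *definitely*.

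**Individual dosing halts (Protocol 11.8.5).** Three statements depend on causality:
- the halt for serious events reads "Participant has a SAE that is possibly or definitely related to drug"
- the halt for severe events that are not serious applies when the "Participant has a non-serious adverse event that is possibly or definitely related to drug and is severe"
- a temporary halt is permitted for a "medically important non-serious AE that is possibly or definitely related to drug and requires medical intervention"

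A fourth, for a serious AE of special interest, has no causality term.

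**Study termination (Protocol 11.8.5).** Three criteria are given as counts of subjects:
- at least 2 "subjects have a SAE that is possibly, probably, or definitely related to drug"
- at least 2 "subjects have a medically important non-serious TEAE that is probably or definitely related to drug and is severe"
- at least 3 "subjects have a medically important non-serious TEAE that is possibly related to drug and is severe"

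**Who decides.** Section 11.8.5 opens by making any decision to stop dosing or terminate a joint one of the Sponsor, Medical Monitor, DSMB and PI after review of the safety data, with the DSMB also able to act alone. Six named parties, from the PI to the FDA, "may pause, halt, or terminate the study at any time following review of any safety concerns". Section 12.10.7.3 gives the DSMB the task of deciding whether stopping rules are triggered, under a charter (Appendix 16) that is not among the documents. Section 12.10.7.4 sends all AEs to the DSMB whatever grade the PI assigned.

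**The concern.** A stopping rule should be readable straight from the grades that investigators record, and stronger evidence of drug causation should never make a stop less likely. As written, section 11.8.5 fails on both counts. It relies on a grade that 12.10.7.4 does not offer and ignores one that it does. In two places its literal wording also reacts to a *possibly* related event but not to the same event graded *probably*.

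Safety is the primary objective, and this is the first patient population to receive the drug, so the DSMB needs a rule with a single reading. Endpoints, estimates and sample size are not affected.

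**Working it through.** No stopping probability is stated for these rules, so there is no plan figure to reproduce. The check sets the wording side by side and then works through the counts.

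**1. Terms in the six causality-based rules, against the reporting scale**

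| Rule in 11.8.5 | possibly | probably | definitely | likely |
|---|---|---|---|---|
| Individual halt, SAE | yes | no | yes | no |
| Individual halt, severe non-serious AE | yes | no | yes | no |
| Temporary halt | yes | no | yes | no |
| Termination, SAE (≥ 2) | yes | yes | yes | no |
| Termination, severe non-serious (≥ 2) | no | yes | yes | no |
| Termination, severe non-serious (≥ 3) | yes | no | no | no |
| *Scale in 12.10.7.4* | *yes* | *yes* | *no* | *yes* |

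*Definitely* appears in 5 of the 6 rules although it is not on the reporting scale. *Likely* is on the scale and appears in 0 of the 6. Neither document maps one scale to the other.

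**2. Individual halts**

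Of the three positive grades open to the investigator, the three halt statements name only *possibly*. Taken literally, changing an SAE from *possibly* to *probably* takes it out of the halt criterion.

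**3. Termination counts for severe, medically important, non-serious TEAEs**

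Let p be the number of subjects whose qualifying event is graded *possibly*, and q the number graded *probably* (or the top grade, once the scales agree). Each subject is counted once.

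- As written: a criterion is met if q ≥ 2 or p ≥ 3.
- Pooled: a criterion is met if q ≥ 2 or p + q ≥ 3.

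| (p, q) | As written | Pooled |
|---|---|---|
| (3, 0) | met | met |
| (2, 1) | **not met** (1 < 2 and 2 < 3) | met (2 + 1 = 3) |
| (0, 2) | met | met |
| (2, 0) | not met | not met |
| (1, 1) | not met | not met |

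The rules differ only where q ≤ 1, p ≤ 2 and p + q ≥ 3 all hold. That forces p = 2 and q = 1, whatever the sample size. Regrading one subject from *possibly* to *probably* moves (3, 0) to (2, 1), so a criterion that was met is no longer met.

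The gap is one subject wide. Up to 3 qualifying subjects can accrue without meeting a criterion as written, against 2 if pooled. From (2, 1), the next qualifying subject gives (3, 1) or (2, 2), and either meets a criterion.

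Because *probably* is on both scales, the (2, 1) result does not depend on how *likely* is mapped.

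**The case against.** The strongest reply is that *possibly* works as a floor throughout 11.8.5. The individual halts pair *possibly* with *definitely* and skip *probably* three times. Since nobody can have meant to halt dosing for a possible relation but not a probable one, the pair is best read as a range, and the third termination bullet as at least possibly related. On that reading (2, 1) counts as three subjects and the gap closes. This is a reasonable reading, but the SAE termination bullet in the same section argues against it: where the drafters pooled the grades, they listed all three. And the floor reading does nothing for the scale mismatch.

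The second reply is that discretion makes the wording matter little. This largely stands. Termination is decided jointly after data review, all AEs reach the DSMB, and the study can be stopped at any time over any safety concern. The (2, 1) case is also narrow. All three events must stay classed as non-serious, although 12.10.7.5 allows important medical events to be classed as serious, and two related SAEs would meet the SAE criterion. The *probably* subject must also have no separate *possibly* related severe event. Section 9.5 reports no clear safety signals so far. Discretion lowers the practical risk, but it does not give the written criteria one meaning.

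A reader might go further and infer that any number of *likely* related events could accrue without a stop. The documents do not support that as the plan's intent. *Likely* is listed first, ahead of *probably*, so any user would treat it as the top grade, and the discretionary powers apply whatever the label.

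**Conclusion.** The concern holds as a wording fault in a safety rule, of minor practical weight.

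- **Scale mismatch:** certain on the text of the two sections, and independent of how the counts are read. The charter or medical monitoring plan (Appendices 16 and 17, not provided) might supply a mapping, but the protocol sections would still disagree.
- **Individual halts:** *probably* is omitted from all three causality-based statements. This matters only on a literal reading, which is unlikely to be what was meant.
- **Termination counts:** out of order in exactly one combination, two *possibly* plus one *probably*, and only if *possibly* is not read as a floor.

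It would be too strong to infer that participants are left unprotected, or that the study would have to continue in the (2, 1) case. The text only fails to list that case as a termination criterion. No probability is attached to it, because the documents give no event rate.

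**What to change.** 1. Use one causality scale in 11.8.5 and 12.10.7.4. The simplest route is to replace *definitely* with *likely* throughout 11.8.5; changing *likely* to *definitely* in 12.10.7.4 would also work. The first route avoids regrading past events only if the AE form already uses the 12.10.7.4 terms, and the form was not provided.
2. Write *possibly, probably, or [top grade]* in the SAE termination bullet and in all three individual halt statements.
3. Keep the bullet requiring at least 2 subjects graded *probably or [top grade]*.
4. Reword the third bullet so that at least 3 subjects count when the event is *at least possibly related (possibly, probably, or [top grade])*.

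Steps 1 and 4 are both needed: pooling without a common scale still leaves *likely* events outside the literal count.

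The cost is a small wording amendment, with the DSMB charter and AE form aligned if they carry the old terms. The termination trigger becomes slightly more cautious, by the one combination shown. Sample size, endpoints and the numerical thresholds do not change.
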